The study will be conducted as a pragmatic, prospective, open-label, multicenter cluster randomized trial where all hospitals in Region Hovedstaden and Region Sjælland will be included. The study will enroll patients during a 2-year period and will run for an additional year to ensure an average follow-up of trial participants of 2 years.

Trial organization and data collection

The sponsor-investigator site, Herley-Gentofte University Hospital, will act as the central organizing trial site which holds overall responsibility for trial conduct, data collection, and quality control. The executive committee is responsible for the scientific aspects of the trial, and represents experienced and skilled trialists, statisticians, and clinicians from the three specialties from which trial patients are recruited. Through collaboration with the Danish Health Data Authority, data on baseline characteristics and endpoints will be collected directly from Sundhedsplatformen and the Danish nationwide administrative healthcare registries. which store data on all healthcare encounters in the universal public Danish healthcare system. Pre-defined diagnosis codes, procedural codes, laboratory sample codes, and Anatomical Therapeutical Classification codes will be used to ascertain endpoints and patient characteristics. Data analysis will be performed at the Department of Public Health, Section of Biostatistics, University of Copenhagen, and treatment assignment will be blinded to the statisticians analysing the trial data. All patient data will be processed and stored in accordance with the General Data Protection Regulation (GDPR), the Data Protection Act, and the Health Act and the appropriate authorities will be properly notified in accordance with applicable rules and regulations. The executive steering committee assumes responsibility to monitor the developments in the therapeutic area closely, and halt the trial if necessary if unanticipated emerging data regarding safety or efficacy indicates that the drugs are no longer able to be considered equivalent. The clinical trial will be conducted in compliance with the protocol, with the Regulation (EU) No 536/2014, and with the principles of Good Clinical Practice. Upon completion of the trial, the anonymized trial data will be shared through a public repository.

Primary endpoint

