The primary endpoint will be the 2-year risk of a composite of death from any cause, hospitalization for HF, myocardial infarction, ischemic stroke, and incident or worsening nephropathy. Incident or worsening nephropathy will be defined as a sustained decrease in estimated glomerular filtration rate (eGFR) of ≥40% from baseline, a sustained decrease in eGFR of ≤10 per minute per 1.73 m2, initiation of dialysis, or kidney transplantation. A broad composite endpoint was chosen to encompass the entire spectrum of benefit shown in outcome trials across the three therapeutic areas of T2D (major adverse cardiovascular events and incident/worsening nephropathy),(7, 8), HF (cardiovascular death, HF, and incident/worsening nephropathy)(1, 2, 4, 20), and CKD (worsening nephropathy and HF).(6, 9) SGLT2-inhibitors have been shown to reduce all-cause mortality in meta

analyses,(21, 22) and this endpoint was chosen rather than cause-specific mortality due to the lack of accuracy in registry-based ascertainment of cause of death. Potential treatment and endpoint heterogeneity will be examined in secondary endpoint and subgroup analyses.

Secondary endpoints

The 2-year risks of the following secondary endpoints will be assessed:

- Death from any cause
- Hospitalization for HF
- Incident or worsening nephropathy
- Myocardial infarction
- Ischemic stroke
- Coronary revascularization
- Hospitalization for unstable angina

Participants

We will include all patients who receive a new prescription for dapagliflozin or empagliflozin during a hospital contact in Region Hovedstaden or Region Sjælland. This includes:

- Patients with T2D
- Patients with HF
- Patients with CKD

Exclusion criteria

- Patients under the age of 18
- Patients who are incapable of giving consent
- Patients who withdraw consent

Treatment

Only empagliflozin and dapagliflozin in regular doses (10 mg) will be included in the study. Prescriptions for empagliflozin 25 mg, dapagliflozin 5 mg, or in combination tablets with other drugs will not be subject to randomization. Nor will other SGLT2-inhibitors, namely canagliflozin, be subject to randomization, as only dapagliflozin

and empagliflozin are approved for treatment of both T2D, HD, and CKD, and can thus be considered equal. Physicians will still be able to prescribe combination products or canagliflozin for T2D, as per usual practice.

Sample size and power

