Based on extrapolations from Danish registry data spanning from 2018 to 2021 (Figure 3), we estimate that 8,600 patients (of whom 30% and 15% will have HF and CKD, respectively), will initiate treatment with dapagliflozin or empagliflozin per year in Region Hovedstaden and Region Sjælland. This will result in randomization of 17,200 patients (8,600 per group) over 2 years. Based on the registry data, we assume a 19% event rate of the primary endpoint during 2 years of follow-up. This will yield 90% power to detect an absolute reduction of 1.9% (corresponding to a 10% relative reduction) in the 2-year rate of the primary endpoint at a statistical significance level of 5%. The expected width of the 95% confidence interval is 2.3%; in other words, the trial can establish that any difference is not larger than 2.3% on the risk difference scale.

Subgroups

We will analyze the primary endpoint in the following subgroups:

- Patients with T2D
- Patients with HF
- · Patients with CKD
- Age <65 years/age ≥65 years
- Males/females

Randomization and blinding

The randomization will be done in clusters which in the present study will consist of 1-hour time frames (Figure 1). In random order, every hour, the treatment assignment will be either dapagliflozin or empagliflozin. A generic module will be developed that allows direct cluster randomization through Epic (Sundhedsplatformen), the EHR platform currently used in Region Hovedstaden and Region Sjælland. The module will alert the physician to the treatment assignment of the current time frame (cluster) when she places a prescription (best./ord.) for either dapagliflozin or empagliflozin. As an example: when a physician makes a prescription for empagliflozin between 11.00 and 11.59 am on a given day, the

randomization module will alert the prescribing physician to which treatment is assigned at the present time frame (cluster). The next hour, the assignment may stay the same or change from e.g., empagliflozin to dapagliflozin in a random fashion. As such, treatment allocation is concealed to patients and caretakers until randomization. In this study design, blinding is not possible to patients and caretakers, but treatment assignment will be concealed to the data collectors and the responsible statistician until the final trial database is locked.

Statistical analyses

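### One kidney criterion of the primary endpoint is worded as an eGFR fall of at most 10 units, so as printed any small sustained fall is a primary event; it probably meant a level reached

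*Protocol*

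**What the plan says.** The Protocol, under Primary endpoint, names this outcome, assessed at 2 years: "composite of death from any cause, hospitalization for HF, myocardial infarction, ischemic stroke, and incident or worsening nephropathy". The kidney component is then defined by two eGFR criteria and two procedures. The first eGFR criterion is "a sustained decrease in estimated glomerular filtration rate (eGFR) of ≥40% from baseline". The rest of the definition is "a sustained decrease in eGFR of ≤10 per minute per 1.73 m2, initiation of dialysis, or kidney transplantation". The same component is listed under Secondary endpoints.

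The other places that name the component (Primary objective, Justification of endpoints) do not define it again, so nothing corrects the second eGFR criterion.

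On ascertainment, Trial organization and data collection says that pre-defined diagnosis, procedure and laboratory codes are applied to health-record and registry data: "laboratory sample codes, and Anatomical Therapeutical Classification codes will be used to ascertain endpoints and patient characteristics". The protocol describes no case-by-case adjudication.

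Under Sample size and power, the planning rate is given as "we assume a 19% event rate of the primary endpoint during 2 years of follow-up", with "randomization of 17,200 patients (8,600 per group) over 2 years" and 90% power for an absolute reduction of 1.9 percentage points.

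**The concern.** The two eGFR criteria share one construction: a sustained decrease *of* some amount. In the first, the amount is at least 40%. In the second, it is at most 10 units. Read as printed, the second criterion is met by any sustained fall above zero and up to 10 units. That is a trivial change for most patients, and the inequality points the opposite way from the one beside it.

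This sits in the primary endpoint and in a secondary endpoint. Because events come from code applied to laboratory data, the written definition is what a programmer works from. If the sentence were coded as it stands, small eGFR changes would count equally with death, heart failure hospitalization, myocardial infarction and stroke. Events of that kind, unrelated to which drug was assigned, shrink any real difference. In a trial whose stated hypothesis is no difference, that dilution favours the expected conclusion.

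**Working it through.** **1. What the printed words do.** The protocol gives no eGFR distribution, so the baselines here are chosen for illustration. In units of mL/min/1.73 m2, the fall needed under each reading is:

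| Baseline | 40% criterion: fall of at least | Second criterion as printed: fall of | Second criterion as a level of 10 or less: fall of at least |
|---|---|---|---|
| 30 | 12 | above 0, up to 10 | 20 |
| 45 | 18 | above 0, up to 10 | 35 |
| 60 | 24 | above 0, up to 10 | 50 |
| 90 | 36 | above 0, up to 10 | 80 |

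At baseline 60, a sustained 3-unit fall (3/60 = 5%) is an event as printed. A 20-unit fall (20/60 = 33%) meets neither eGFR criterion. A 24-unit fall (24/60 = 40%) is an event again. A rule under which a small fall counts and a larger one does not cannot be the intended one. Read as a level, the criterion is met only by advanced loss of function, which fits its place beside dialysis and transplantation.

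**2. The plan's own power.** Inputs from Sample size and power: n = 8,600 per group, p1 = 0.19, p2 = 0.19 − 0.019 = 0.171, alpha 5%. The protocol does not state whether alpha is one- or two-sided; two-sided reproduces its figure.

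Power = Φ[(p1 − p2 − 1.96·s0)/s1], where s0 = √(2·p̄(1 − p̄)/n), p̄ is the mean of p1 and p2, and s1 = √((p1(1 − p1) + p2(1 − p2))/n).

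- p̄ = 0.1805, s0 = 0.005865, s1 = 0.005863
- (0.019 − 1.96 × 0.005865)/0.005863 = 1.28, so power = 0.900

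The stated 90% is reproduced.

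**3. Illustration of dilution.** Assumption, not in the documents: a share q of patients who would otherwise have no event meets the literal criterion, the same in both arms. Then p1 = 0.19 + 0.81q and p2 = 0.171 + 0.829q, and the difference is 0.019 × (1 − q).

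| q | p1 | p2 | Difference | Relative reduction | Power |
|---|---|---|---|---|---|
| 0 | 19.0% | 17.1% | 1.90 points | 10.0% | 0.900 |
| 10% | 27.1% | 25.4% | 1.71 points | 6.3% | 0.722 |
| 20% | 35.2% | 33.7% | 1.52 points | 4.3% | 0.555 |
| 30% | 43.3% | 42.0% | 1.33 points | 3.1% | 0.422 |

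The direction follows from the wording. The size depends entirely on q, which the protocol does not give.

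**4. Effect of the correction on sample size.** None. The 19% is an assumed rate, so 8,600 per group and 90% power stand if that rate was obtained with the intended definition.

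**The case against.** The strongest reply is that this is an obvious slip of one preposition. The literal rule is incoherent, the neighbouring items point to a level, and the executive committee includes statisticians and clinicians from all three specialties. Nothing shows that anyone will code the sentence literally. All of that is fair, and literal coding is a risk, not a prediction. It does not remove the need to correct the text. A second small edit is also possible, a fall of *at least* 10 units. At baseline 60 that would require a fall of 10 units, against 50 for the level reading. These are very different endpoints, and a primary endpoint should not leave the choice to inference. Nor can the point be left to an SAP: the protocol states the rule wrongly, and an SAP that used a level would contradict it.

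Several stronger readings are tempting but not supported:

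- **That the wording harms the trial by leaving larger falls uncounted.** A sustained fall from 90 to 60 (33%) is not an event as printed. It would still not be one after the criterion is reworded as a level, because it is below 40% and does not reach 10. The gap shows that the printed rule is incoherent; it is not a loss that the correction repairs.
- **That the composite would rise to some particular rate.** Shares of one third or one half of event-free patients would give 1 − 0.81 × 2/3 = 46% and 1 − 0.81 × 1/2 = 60% (59.5% before rounding). Nothing in the protocol supports those shares. The 10% to 30% used above is no better founded and serves only as illustration.
- **That the 19% planning rate is void.** Figure 3 is captioned as showing event rates of the primary endpoint in registry data, so some working definition was already applied. Which one cannot be seen, and no mismatch is shown.
- **That the printed unit, which lacks a volume, is a further error.** Conversion of the text from PDF may explain it.
- **That the baseline value is unreliable.** How baseline is fixed is a separate matter, commonly left to the SAP.

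**Conclusion.** The criterion is wrong as written. The printed definition makes any sustained eGFR fall of up to 10 units a primary event and a secondary event, and no other part of the protocol corrects it. A level of 10 or less is the likely intention, inferred from context and not stated. If coded literally, the criterion would dilute the comparison towards no difference. By how much cannot be derived from the protocol; the drop from 90% to between about 72% and 42% power rests on the assumed 10% to 30%, equal in both arms. The correction is needed because the sentence defines the primary endpoint, not because of those figures. The stated sample size and power are not themselves in error on this account.

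**What to change.** The sponsor should first confirm whether the 10 is a level reached or the size of a change. If it is a level, as seems likely, replace the criterion in Primary endpoint with wording such as *a sustained eGFR of ≤10 mL/min/1.73 m2*. Carry the same rule into the endpoint code for both the primary composite and the secondary nephropathy endpoint. Then check that the registry code behind Figure 3 and the 19% rate used this definition, and revisit the planning rate only if it did not.

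The cost is one line of protocol text, a matching line of code where needed, and a look at existing registry code. No change to sample size or data collection follows from the rewording itself.

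### As written, any start of dialysis counts as a kidney event, including temporary dialysis with recovery, although the eGFR criteria beside it must be sustained

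*Protocol*

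**What the plan says.** Under Primary endpoint, the protocol lists four ways to meet incident or worsening nephropathy. Two rest on kidney function: "a sustained decrease in estimated glomerular filtration rate (eGFR) of ≥40% from baseline" and "a sustained decrease in eGFR of ≤10 per minute per 1.73 m2". The other two are "initiation of dialysis, or kidney transplantation". The word sustained belongs to the eGFR criteria only. Nothing in the section says that dialysis must be chronic, must last a minimum time, or must be for a particular indication.

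The same kidney definition serves twice: as a component of the primary composite and as a secondary endpoint of its own.

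Under Trial organization and data collection, ascertainment is by code: "Pre-defined diagnosis codes, procedural codes, laboratory sample codes, and Anatomical Therapeutical Classification codes will be used to ascertain endpoints". The codes are not listed. No event adjudication is described.

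Under Participants, recruitment is broad: "We will include all patients who receive a new prescription for dapagliflozin or empagliflozin during a hospital contact". The Sample size section expects 30% of patients to have HF and 15% to have CKD. None of the three exclusion criteria concerns kidney function or dialysis.

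**The concern.** Requiring a sustained eGFR fall keeps reversible kidney injury out of the endpoint. The dialysis alternative lets it back in. A patient who receives a short course of dialysis during a critical illness and recovers fully meets the definition. A patient with an equally deep, equally reversible eGFR fall who is managed without dialysis does not.

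The Primary endpoint and Justification of endpoints sections justify the kidney component by the renal benefits seen in outcome trials of this drug class. Dialysis for an unrelated acute illness, with recovery, is not that kind of event.

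Three features of this trial make the point worth settling:

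- Patients are recruited through hospital contacts, and many will have HF or CKD, so acute dialysis is plausible, although the protocol gives no rate.
- Under Statistical analyses, follow-up runs until the primary outcome. A temporary dialysis event would therefore end a patient's follow-up for the composite and hide a later genuine event.
- The stated hypothesis is that the drugs do not differ significantly. Events that have nothing to do with the choice of drug move the hazard ratio towards 1, the direction that favours this hypothesis.

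**Working it through.** **Inputs from the protocol (Sample size and power).** 8,600 patients per group; 19% two-year risk of the primary endpoint; absolute reduction of 1.9 points, so 19.0% versus 17.1%; 5% significance level, taken as two-sided; stated power 90%.

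**Assumptions, not in the documents.** Let *k* be the two-year risk, the same in both arms, of a primary event that consists only of temporary dialysis. Values of 0.2%, 0.5% and 1.0% are used (17, 43 and 86 patients per arm). For the kidney endpoint alone, assume a genuine two-year risk of 3% and a true relative risk of 0.90.

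**Step 1: the plan's own figure.** For two proportions with pooled variance under the null,

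power = Φ{[(p1 − p2)√n − 1.96√(2p̄(1 − p̄))] / √(p1(1 − p1) + p2(1 − p2))}.

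With p1 = 0.190, p2 = 0.171, p̄ = 0.1805 and n = 8,600: (1.762 − 1.066)/0.5437 = 1.280, and Φ(1.280) = 89.97%. The stated 90% is reproduced.

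**Step 2: the composite.** There are two ways to place the extra events.

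- *Added on top of the 19%:* compare 0.190 + *k* with 0.171 + *k*. The absolute difference stays at 1.9 points and only the variance grows.
- *Within the 19%:* the genuine part is 0.190 − *k* and keeps its 10% reduction. Compare 0.190 with 0.9 × (0.190 − *k*) + *k*. The absolute difference shrinks to 0.1 × (0.190 − *k*).

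| *k* | Added: risks | Added: power | Within: risks | Within: power |
|---|---|---|---|---|
| 0.2% | 19.2% v 17.3% | 89.72% | 19.0% v 17.12% | 89.35% |
| 0.5% | 19.5% v 17.6% | 89.36% | 19.0% v 17.15% | 88.35% |
| 1.0% | 20.0% v 18.1% | 88.75% | 19.0% v 17.20% | 86.56% |

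Against 89.97%, the loss is 0.25 to 1.2 points in the first case and 0.6 to 3.4 points in the second. The observed relative risk moves from 0.900 to 0.905 at most.

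**Step 3: the kidney endpoint.** Observed relative risk = (0.03 × 0.9 + *k*)/(0.03 + *k*). Share of events that are unrelated, in the arm with the 3% risk = *k*/(0.03 + *k*).

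| *k* | Observed relative risk | Unrelated share |
|---|---|---|
| 0.2% | 0.029/0.032 = 0.906 | 6% |
| 0.5% | 0.032/0.035 = 0.914 | 14% |
| 1.0% | 0.037/0.040 = 0.925 | 25% |

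**Step 4: scale against sampling error.** With 3% and 2.7% of 8,600 there are 258 and about 232 kidney events. The standard error of the log relative risk is √(1/258 + 1/232 − 2/8,600) = 0.089, so the 95% interval around 0.90 is about 0.76 to 1.07. The shifts in step 3 are small beside that.

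**The case against.** The strongest reply is that this is operational detail. Endpoints are to be read from pre-defined codes, and a code list or SAP that is not at hand may already restrict dialysis to chronic codes. The protocol does not say how long sustained means either, so it may be working at headline level. This stands in part. A reader might infer that temporary dialysis will certainly be counted, and the documents do not support that; they support only that it would count if the definition is followed as written. But the protocol does not leave the definition open. It states one, and a narrower code list would then differ from it.

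A second reply is that the protocol deliberately chose a broad endpoint. That choice is explained as covering the whole range of potential clinical benefit. It does not speak to reversible acute injury, which the eGFR criteria exclude.

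A third reply is that the effect is small and rests on assumed rates. This stands for the composite. Some patients given acute dialysis will die and count through death in any case, so the net excess is smaller than the number dialysed. The direction is also conditional: dilution follows only if acute dialysis does not depend on which of the two drugs was given, which the documents do not establish.

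A reader might also infer that patients already on dialysis at enrolment would be counted as events, since no exclusion covers them. The wording does not support this, because such a patient does not initiate dialysis. Prior dialysis could be sought in the registries and EHR that supply the baseline data. A look-back before randomisation is worth noting for ascertainment, but it is not a fault in the definition.

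**Conclusion.** The point holds as a flaw in a stated definition: reversible injury is kept out by two of the kidney criteria and admitted by a third, in both the primary composite and the secondary nephropathy endpoint. The case rests on that inconsistency more than on lost power.

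The effect on the composite is small: at most about 1.2 points of power if temporary dialysis in up to 1.0% of patients is added to the planned risks, and about 3.4 points if the same 1.0% lies within the 19%. The effect is proportionally larger for the kidney endpoint, where up to a quarter of events could be unrelated and a relative risk of 0.90 could appear as 0.925. All of this assumes equal temporary-dialysis rates in both arms, unaffected by the drug, and a 3% genuine kidney risk; the documents give none of these. A reading that the primary comparison is seriously compromised would go beyond the evidence.

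**What to change.** In the Primary endpoint section, replace the dialysis alternative with initiation of maintenance (chronic) dialysis after randomisation, identified by a chronic-dialysis code or by a pre-specified minimum duration. Twenty-eight days would serve as an example; the documents give no basis for a particular figure. State that temporary dialysis counts only if a sustained eGFR criterion is also met. Leave transplantation as it is. Align the code list with this wording, and note there that a registry look-back separates new from ongoing dialysis.

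The cost is one line of text and a choice of codes, with no new data. There is one real downside. A duration rule makes the event depend on surviving long enough to meet it. Patients with true kidney failure who die earlier still count in the composite through death, but may be lost from the secondary kidney endpoint unless their dialysis is coded as chronic. Accepting a chronic code as an alternative to duration limits that loss.

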- 2. The organization of training at local departments which includes physical meetings, presentations and webinars about the study. This focuses mainly on prescription of the study drugs in the randomization module in Sundhedsplatformen, as administration of either drug will not differ from current clinical practice.
- 3. The organization and monitoring of changes in Sundhedsplatformen and the software module.

Patient insurance

Insurance of patients is secured through Patienterstatningen.

Financing

The patients will have no extra costs in relation to the trial, as SGLT2-inhibitors are administered free of charge at the hospitals or purchased through a regular prescription at the pharmacy. The hospitals and patients will not have substantial additional costs, since dapagliflozin and empagliflozin currently have equal market shares in Denmark. Currently, empagliflozin costs 16 DKK/DDD for the 10 mg dosis, while dapagliflozin costs 17 DKK/DDD for the 10 mg dosis. Prices are not expected to change until expiration of the patents (2028), by when completion of follow up is planned to have occurred. In the event of price changes for two consecutive two week periods leading to a ≥1000 DKK per annum difference compared to the current price difference between empagliflozin and dapagliflozin, the executive steering committee will inform enrolled study participants about the price difference through E-boks. As only patients already being prescribed either empagliflozin or dapagliflozin will be enrolled in the study, and current choice of either drug is arbitrary, enrolment in the study will not incur extra cost to patients. The costs related to operating the trial are relatively modest and consist of consultation fees for software developers within EPIC, production of informational material, and employment of PhD fellows and postdocs. These costs are covered by an independent research grant of DKK 5,053,553 from the Novo Nordisk Foundation, Investigator Initiated Clinical Trials Grant: A Pragmatic Trial Comparing Empagliflozin and Dapagliflozin Through Cluster Randomization Embedded in the Electronic Health Record (APPLE TREE) - NNF23OC0085981.

Timeline

2023 Q3-Q4: Application for funding.

2024 Q1-Q2: Approval by authorities, information meetings at participating

departments, preparation of study initiation.

2024 Q3: First patient enrolled.

2026 Q4: Last patient enrolled (December 31).

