2027 Q4: End of follow-up (December 31). After the last patient is enrolled, outcome data will be collected from the registries for an additional year before database lock, to ensure an average follow-up time of 2 years for all study participants.

2028 Q1-: Presentation of results and publication.

Figures

[figure not shown]
[figure not shown]

Figure 2: Comparison of cluster RCTs and traditional RCTs. RCT, randomized controlled trial.

Initiators of dapagliflozin or empagliflozin between 1/2018 and 7/2021 (2322 with HF, 1722 with CKD)

Subjects: 21214 20999 20855 20591 18403 16539 14911 13450 12514 11426 10313

Initiators of dapagliflozin or empagliflozin between 1/2020 and 7/2021 (1652 with HF, 1086 with CKD)

[figure not shown]

Figure 3: Event rates of the primary endpoint in patients initiating empagliflozin and dapagliflozin in Eastern Denmark between January 1st, 2018 and July 31st, 2021. Data were extracted from the Danish nationwide registries. During this period, most patients initiating empagliflozin or dapagliflozin had type 2 diabetes without heart failure or chronic kidney disease. As guidelines are implemented in clinical practice, it is expected that more patients with heart failure and chronic kidney disease will initiate empagliflozin and dapagliflozin, leading to higher anticipated event rates than those observed between 2018 and 2021.

References

- 6. The E-KCG, Herrington WG, Staplin N, Wanner C, Green JB, Hauske SJ, et al. Empagliflozin in Patients with Chronic Kidney Disease. N Engl J Med. 2023;388(2):117-27.

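### The planned 17,200 equals every projected initiator in the two regions over two years, with no allowance for the patients that the protocol's own enrolment rules leave out

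*Protocol*

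**What the plan says.** **Projection.** The Sample size and power section, extrapolating from Danish registry data for 2018 to 2021, estimates that 8,600 patients "will initiate treatment with dapagliflozin or empagliflozin per year in Region Hovedstaden and Region Sjælland". The next sentence reads: "This will result in randomization of 17,200 patients (8,600 per group) over 2 years".

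**Power and precision.** The same section states "we assume a 19% event rate of the primary endpoint during 2 years of follow-up" and then "This will yield 90% power to detect an absolute reduction of 1.9% (corresponding to a 10% relative reduction", at a 5% significance level. It gives an expected 95% confidence interval width of 2.3%.

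**Who can be enrolled.**
- Participants: "We will include all patients who receive a new prescription for dapagliflozin or empagliflozin during a hospital contact". Patients under 18 and those who cannot consent are excluded.
- Treatment: "Prescriptions for empagliflozin 25 mg, dapagliflozin 5 mg, or in combination tablets with other drugs will not be subject to randomization".
- Recruitment arrangements: a patient counts as enrolled only once the randomisation is accepted in the module; those who opt out there are not enrolled.
- Withdrawal of consent: data of patients who withdraw are not analysed, and a message one month after discharge reminds every participant of this option.

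**Duration.** Trial design gives a two-year enrolment period. The Timeline puts the first patient in 2024 Q3 and closes with "2026 Q4: Last patient enrolled (December 31", a calendar date.

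**The concern.** The starting figure counts people who begin either drug in two regions. Neither the Sample size section nor the Figure 3 caption limits that count to hospital prescriptions, to 10 mg single-agent tablets or to people who would accept randomisation. The enrolled population is limited in all of these ways, and the analysed population is reduced again by withdrawal. Each rule can only lower the number, yet the number randomised equals the number projected.

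The size, power and interval width in this section are therefore tied to complete capture. Enrolment closes on a date, and no target number of patients or events is stated that would keep it open if accrual fell short. A reader planning around 90% power and a 2.3-point interval should know that both assume no loss at all over the stated two years.

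**Working it through.** **Inputs from the protocol.** 8,600 initiators per year; 2 years; equal groups; 2-year risk 19.0% against 17.1% (19.0% less 1.9 points); 5% significance, taken as two-sided because that reproduces the stated power.

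**Input not in the protocol.** The capture fraction *f*, meaning analysed patients divided by projected regional initiators. It is an assumption and is shown over a range.

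**Step 1: the number.** 8,600 × 2 = 17,200, or 8,600 per group. The implied *f* is 100%.

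**Step 2: reproduce the stated power.** For the two-proportion z-test with *n* per group and mean risk (0.19 + 0.171)/2 = 0.1805:
- standard error under no difference: √(2 × 0.1805 × 0.8195 / 8,600) = 0.005865
- standard error under the alternative: √((0.19 × 0.81 + 0.171 × 0.829) / 8,600) = 0.005863
- z = (0.019 − 1.96 × 0.005865) / 0.005863 = 1.280, so power = 89.97%

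Solving the same formula for *n* gives 8,609 per group for 90% power and 6,431 for 80%. The plan's figure reproduces, and 8,600 leaves no reserve.

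**Step 3: reproduce the stated width.** Full width = 2 × 1.96 × 0.005863 = 2.30 points. The quoted 2.3% is the full width, not the half-width.

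**Step 4: vary capture over the stated two years.** N = 17,200 × *f*, with the event rates held at 19.0% and 17.1%.

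| Assumed capture | N | Power | Full 95% CI width |
|---|---|---|---|
| 100% | 17,200 | 89.97% | 2.30 points |
| 90% | 15,480 | 86.7% | 2.42 points |
| 80% | 13,760 | 82.6% | 2.57 points |
| 70% | 12,040 | 77.4% | 2.75 points |

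Power falls below 80% once capture drops under about 75% (6,431 / 8,600).

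**Step 5: use the Timeline's window.** From 2024 Q3 to 31 December 2026 is 2.25 to 2.5 years, depending on when in that quarter the first patient enters.
- Projected initiators: 8,600 × 2.25 = 19,350; 8,600 × 2.5 = 21,500.
- Capture that still yields 17,200: 17,200 / 19,350 = 89%; 17,200 / 21,500 = 80%.
- At 80% capture: N = 15,480 to 17,200, power 86.7% to 90.0%.
- At 70% capture: N = 13,545 to 15,050, power 82.0% to 85.8%.

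The longer window therefore absorbs a loss of about 11% to 20%. Beyond that, power is again below 90% and the width above 2.3 points.

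**The case against.** **The timeline gives slack.** This stands in part. On the Timeline's dates the trial could lose a tenth to a fifth of initiators and still randomise 17,200. But the sample size statement is for two years, Trial design says two years, and nowhere is the longer window offered as an allowance. It is a conflict to reconcile, and it does not cover a larger loss.

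**The shortfall cannot be computed.** This stands. The protocol gives no share for hospital prescribing, for the 10 mg products, for opt-out or for withdrawal, and it does not say whether the extrapolation was already restricted to eligible prescriptions. The wording reads as unrestricted. Even a restricted count would still need an allowance for opt-out and withdrawal.

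**The event rate may differ too.** This stands. Patients treated at hospitals need not have the 19% risk assumed. If their risk were about 23% (an assumption), a 10% relative reduction would have about 90% power even at 80% capture over two years. A lower risk would make matters worse. The protocol does not settle the direction.

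**Stronger readings that the protocol does not support.**
- A reader might infer that a null result would be over-read. It would not follow: 2.3 points is the full width, so with a zero estimate the half-width stays below 2.3 points down to roughly 4,500 patients (about 26% capture over two years). The section's remark on the largest difference that could be missed is cautious at every capture level tabulated.
- A reader might also treat the growth and case mix as errors: 8,600 per year against 21,214 over 43 months, and 30% HF and 15% CKD against lower registry shares. The section calls these extrapolations. The Figure 3 caption says "During this period, most patients initiating empagliflozin or dapagliflozin had type 2 diabetes without heart failure or chronic kidney disease" and explains why more HF and CKD patients are expected. The figure's own counts show the rise: 1,652 of 2,322 HF initiators and 1,086 of 1,722 CKD initiators fall in the last 19 months.

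**Conclusion.** The concern holds in a limited form. As written, the section equates projected initiators with randomised patients, although the protocol's own rules leave some of them out, and it states no allowance. The stated size, power and width hold over two years only at 100% capture. At 90%, 80% and 70% capture, power is about 3, 7 and 13 percentage points below the stated 90%.

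These figures rest on the assumed capture fractions, on event rates held at 19.0% and 17.1%, and on the stated two-year enrolment. On the Timeline's dates, the stated figures survive a loss of about 11% to 20%.

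A reader might go further and conclude that the trial will be underpowered. The protocol does not show that: neither the capture fraction nor the event rate of the randomisable population is given, and the enrolment window is itself stated inconsistently. What can be said is that the basis for 17,200, 90% and 2.3% is incomplete.

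**What to change.** In the Sample size and power section, and consistently in Trial design and Timeline:

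1. Reconcile the enrolment duration (two years against 2.25 to 2.5 years), and say whether enrolment ends on the date alone or also depends on a target number.
2. Base the projection on prescriptions that the module can randomise: adults, new prescription during a hospital contact, 10 mg single-agent product. If the 8,600 was already restricted in this way, say so.
3. State an allowance for patients who cannot consent, for opt-out and for later withdrawal, with its basis.
4. Restate the expected number, the event rate in that population, the power and the full interval width. If the capture fraction is unknown, give these over a range, as in the table above.

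The cost is a further query of the registry or health-record data and revised wording in a few places. No extra patients and no change to the randomisation or analysis are required. The downside is that the restated power and precision may be less favourable than 90% and 2.3%.
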